Version Date: 3/2/2018

Principal Investigator: [name]

Co-Investigator: [name]

Study Physician: [name]

Study Title: Body Fat Reducing Effect and Safety of Enzymatically Modified Isoquercitrin in Overweight and Obese Subjects

I. Aim and Hypotheses

Specific Aim 1: To compare the body fat reducing effect of 360mg/day enzymatically modified isoquercitrin (EMIQ) with that of a placebo.

Hypothesis 1: Compared to a placebo, participants receiving EMIQ supplementation will have a greater reduction in total body fat as evidenced by measures of whole body DXA scan, skinfold thickness, waist to hip circumference ratio, resting metabolic rate, plasma adiponectin levels, physical activity, and dietary intake.

Specific Aim 2: To determine the safety of long term intake of EMIQ.

Hypothesis 2: Long-term intake of EMIQ has no ill effect on participant health as evidenced by measures of heart, liver, kidney function, and psychological state.

II. Background and Rationale

Dietary quercetin is a natural bioactive polyphenol with potential health benefits and the capacity to prevent development of various diseases including those of the cardiovascular system, central nervous system and others [1-3]. It is widely distributed in various plant foods such as onions, broccoli, concord grapes, apples and more [4]. In plants, quercetin is present as conjugated with different forms of glucosides [5], which affect their bioavailability. The bioavailability of different forms of quercetin has been the subject of several investigations [6]. Enzymatically-modified isoquercitrin (EMIQ) is a mixture of quercetin monoglucoside and its α -oligoglucosides, which mainly consist of quercetin-3-O- β -glucoside (Q3G) and α -glucosyl derivatives with 1-7 of additional linear glucose moieties [7, 8]. Supplementing the diet of apoE-deficient mice with EMIQ increased quercetin levels and suppressed atherogenesis in this mouse model of human atherosclerosis[9]. In human trials, the bioavailability of EMIQ

has been shown to be 17-fold higher than quercetin aglycone [10]. After efficient absorption of EMIQ, quercetin is released, and it exerts its biological activity such as reducing body fat, improving cardiovascular health and reducing blood pressure.

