 - HIV or AIDS based on self-report.
 - Steroid use with the exception of over-the-counter topical and nasal steroids such as Flonase.
 - Allergy medication or regular antihistamine use.

- Seizure disorders. Acceptable if managed with medication and free of seizure activity for 5 years.
 - Smoking or the use of nicotine replacement products in the past 6 months.
 - Use of dietary supplements containing vitamins (except Calcium and Vitamin D), minerals, herbal or plant-based preparations, fish oil or homeopathic remedies during study participation unless willing to discontinue prior to enrollment.
 - Current participation in another research study.
 - Non-English speaking.
 - No social security number.
 - Participation in another research study.
- **Withdrawal/Termination Criteria:** Low compliance including taking less than 80% of study supplements, or missing study visits. Subjects who manifest an allergic reaction to the study supplement or placebo. Negative health effects as determined by the study physician. In the event of a withdrawal/termination, study subjects will be asked to discontinue their study supplement, and, if necessary due to negative health effects, will be referred to their primary care physician.

*Note: Screening lab values that would interfere with study outcomes are determined at the discretion of the study physician.

D. Risk/Benefit Assessment: We do not anticipate any major risks or hazards to participants in this study.

There are no benefits to participation in this study. EMIQ has been independently evaluated by an expert panel as safe and has been categorized as GRAS (generally recognized as safe) according to the Food and Drug Administration (FDA)(see attachment “5. FDA GRAS EMIQ”). Other investigators have conducted similar clinical studies with EMIQ at doses comparable to those in this study and reported no adverse effect.

While all measures to ensure confidentiality will be taken, it is an ever present possibility that it may be lost. Stored samples will be labeled with a unique number (code) that will not contain any private information such as name or date of birth to ensure the samples cannot be identified. There is no intention for allowing anyone other than the principal investigator to have access to these codes. If [name] turns this study over to a new principal investigator, he will give the key code to the new principal investigator.

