Study participants will be contacted by a member of the study team each week either by phone or by email to monitor adherence to the intervention and to monitor self-reported health changes. Study team members will fill out a weekly log to ensure that volunteers have been contacted. If any abnormalities are reported, the study physician will be informed. The study physician will advise the participant to follow up with their primary care physician and also decide if the participant can continue with the intervention.

Participants will receive a compliance calendar used to track their supplement intake at visit 2.

Participants will be required to return any unused supplements and compliance calendar at visits 3, 4 and 5. Participants that miss a visit beyond the allowed interval (4 weeks \pm 1 week from previous visit) will be instructed to discontinue their supplement, if they have not done so already, and they will be removed from the study.

V. Location

This study will be performed at the Metabolic Research Unit and Vascular Biology Laboratory at the Jean Mayer USDA Human Nutrition Research Center on Aging at Tufts University, located at [name].

DXA scans will be performed at the Body Composition Analysis Center at Tufts University Friedman School of Nutrition and Science Policy, located at [name].

VI. Transportation

Volunteers will be required to provide their own transportation to the HNRCA. The building is accessible by public transportation. However, if

participants should choose to drive, they can obtain parking validation at a reduced cost.

VII. Personnel who will conduct the study

a. Present During Study Procedures:

Study Nurse
Study Coordinators
Principal Investigator

b. Primary Responsibility for the Following Activities

i. Obtaining Informed Consent

Authorized MRU staff
Principal Investigator
Study Coordinators

ii. Providing On-Going Information to the Study Sponsor and the IRB

Principal Investigator
Co-Investigator
Study Physician

iii. Maintaining Participant's Research Records

Authorized MRU staff
Principal Investigator
Study Coordinators

VIII. Subject Payment

Screening Stipend: \$25

Visit 1 Stipend: \$50

Visit 2 Stipend: \$150

Visit 3 Stipend: \$50

Visit 4 Stipend: \$50

Visit 5 Stipend: \$305

Subjects will only be paid for each completed visit, and will not be paid if they withdraw or are withdrawn from the study.

IX. Confidentiality

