Participants and nursing staff will be able to reach the study physician, [name], or a covering physician 24 hours/day. Specific participant complaints will be addressed on an individual basis and appropriate referrals to primary care providers or other health care providers will be made. Participants' health status will be assessed weekly through phone or email and will be updated by the members of the study team. While there is no evidence to suggest so, there might be some adverse effects from EMIQ's effect on fat loss, or EMIQ itself. If these problems are reported by participants, the condition will be assessed to determine if these adverse events are potentially study-related. Further, in the case of these and any other adverse event, the study physician will advise participants on the appropriate assistance or action to take, and then counseled to seek further appropriate assistance.

Compensation will not be available for any research-related injury, and treatment may incur charges for the subject. The Nursing staff at the MRU is basic BLS (CPR) certified and trained in the use of an automatic external defibrillator (AED). In all emergency situations, the MRU Nursing staff will provide immediate basic life support (BLS) response, call 911 and continue to provide emergency supportive care as needed (e.g., monitoring, oxygen, airway maintenance) until emergency medical service (EMS) arrives. Their philosophy is to provide early access to the most appropriate and advanced care for treatment of study subjects. Treatment by the MRU Nursing staff and/or the staff physician is provided at no cost to the participants. All additional treatment including the cost of an ambulance is charged to the study subject. There are no funds available for these costs to be paid by the HNRCA or by study funds. This information is provided to participants prior to their signing an informed consent form.

A participant may be dropped from the study should a reported adverse reaction to the study supplement be considered severe.

G. Subject Safety and Data and Safety Monitoring Plan

Classification and Reporting of Adverse Events and Unanticipated Problems for This Study

An **Unanticipated Problem** is defined as: An incident, experience, or outcome that meets all of the following criteria:

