1. The nature, severity, or frequency is unexpected for the subject population or research activities as described in the current IRB approved protocol, supporting documents, and the ICF(s).
2. It is related or possibly related to participation in the research.
3. It suggests the research may place the subject or others at a greater risk of harm than was previously recognized.

An **Adverse Event (AE)** is defined as: Any untoward or unfavorable medical occurrence in a human subject, including any abnormal physical exam or laboratory finding, symptom, or disease, temporally associated with a subject’s participation in the research.

AEs are classified by three categories:

1. Severity: *Non-serious* or *Serious*
2. Relation to Participation in Research: *Related, Possibly Related, or Unrelated*

The classification of the potential relationship to the intervention will be determined based on the following scheme:

Definite	Temporal pattern and known or expected adverse event response pattern, confirmed by stopping the intervention and reappearance of adverse event on re-challenge.
Probable	Temporal pattern and known or expected adverse event response pattern, confirmed by stopping the intervention and which could not be explained by the participant’s clinical state.
Possible	Temporal pattern and known or expected adverse event response pattern, confirmed by stopping the intervention and which could have been produced by a number of other factors.
Unknown	Relationship for which no evaluation can be made.
Not Related	Adverse event for which sufficient information exists to indicate that the cause is unrelated to the study intervention.

3. Expectation: *Expected* or *Unexpected* (determination is based on the known risks associated with the study supplement and procedures, natural progression of an underlying illness, and health characteristics of the study population)
4. Location: *Internal* (occurring at the HNRCA) or *External* (occurring at a site that is not under the jurisdiction of the Tufts MC/TUHS IRB)

Further, a **Serious Adverse Event (SAE)** is an **AE** that meets the following criteria:

1. Results in death, or
2. Is life-threatening, or
3. Results in hospitalization or prolongation of existing hospitalization, or
4. Results in a persistent or significant disability/incapacitation, or
5. Results in congenital anomaly/birth defect, or

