- [name] will regularly monitor potential risks and procedures in order to protect participants from risk.
- Will discuss any adverse events with the study physician on a weekly basis.
- Will report any adverse events associated with participation in the study protocol and file all required annual paperwork with the IRB.
- Will evaluate the progress of the study including periodic assessments of data quality and timeliness, recruitment, enrollment and retention, protocol violations, unanticipated events, volunteer risk vs. benefit, and anything else that may have an impact on the study outcome.
- Maintain vigilance of developments outside of the study that could affect participant's safety.
- Perform, at minimum, two reviews of the data per year to ensure safety and efficacy of the study.
- Responsibility for all procedures performed.
- Reviews all data as it may relate to volunteer safety. This includes factors like participant retention and reason for drop-out.
- Reporting all serious adverse events regardless of their relation to the study protocol.
- Provide the IRB with summaries of all adverse events.
- At the discretion of [name], the Co-I, [name], or [name], the study may be terminated at any time if the risks to study subjects are found to outweigh the potential benefits.

Additionally, no personal results will be communicated to study participants. However, participants will be informed of any necessary new findings developed during the course of this research study. Written results may be given directly, or mailed, to participants if they are still in the study, or mailed to them if they have completed their participation in the study.

H. Outcome

Our goal is to assess the safety and efficacy of EMIQ as it relates to body fat reduction. We predict that there will be no changes in health, and that there will be a significant difference between change in total body fat between the treatment and placebo groups.

I. Tissue Banking Considerations

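### The safety claim is general, but the evidence named for it omits adverse events, and the completers-only analysis set leaves out subjects withdrawn for harm

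*Protocol*

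**What the plan says.** **The claim is broad.** Protocol section I states Aim 2 as "To determine the safety of long term intake of EMIQ". Section III.H (Outcome) says "We predict that there will be no changes in health".

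**The named evidence is narrower.** Hypothesis 2 in section I reads "Long-term intake of EMIQ has no ill effect on participant health as evidenced by measures of heart, liver, kidney function, and psychological state". Adverse events are not among these measures.

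**Adverse events are collected.** Under Compliance (III.E.IV), participants are "contacted by a member of the study team each week either by phone or by email", partly to pick up self-reported health changes. Volunteer Consent and Safety (III.F) repeats that "health status will be assessed weekly through phone or email". Section III.G defines an adverse event widely, "including any abnormal physical exam or laboratory finding, symptom, or disease", and classifies events by seriousness and relation to the intervention.

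**Their stated uses are oversight.** They serve the physician's handling of the individual case, weekly discussion between the investigator and study physician, IRB reporting ("Provide the IRB with summaries of all adverse events") and possible early termination of the study.

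**Harm can remove a subject.** The withdrawal criteria (III.C) include "Subjects who manifest an allergic reaction to the study supplement or placebo", and negative health effects as judged by the study physician. Section III.F adds that a severe adverse reaction may lead to a subject being dropped.

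**The analysis text is silent on adverse events.** Protocol III.B covers body weight and fat outcomes. The SAP analyses subjects who completed the study and gives Fisher's exact or chi-square tests for categorical variables in general, without naming adverse events or any separate safety set.

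**The concern.** Safety is in the study title and is one of two specific aims. In a supplement trial in volunteers, reported symptoms, allergic reactions and stops because of an event are the most direct evidence of harm. The protocol foresees harms outside its four domains: it accepts that EMIQ or the fat loss itself might have adverse effects, and it makes allergic reaction a reason for withdrawal.

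Followed as written, the plan could report no ill effect on health without ever setting the two arms' adverse events side by side. It could also do so in a set from which the subjects most likely to have been harmed have been removed.

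**Working it through.** **1. The plan's own figure.** The only sizing figure is for efficacy. With d = 19 − 1 = 18 and S = (24.62 + 12.87)/2 = 18.745, N = 1 + 16 × 18.745²/18² = 1 + 17.35 = 18.35, which reproduces the stated 18 per group. There is no safety figure to reproduce: no event rate, margin or criterion is given.

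**2. What the four domains can register.**

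| Domain | Main measures in the protocol | Would it record a rash, gastrointestinal complaint, headache or infection? |
|---|---|---|
| Heart | EKG at visits 2 and 3; blood pressure and heart rate | No |
| Liver | Enzymes and related blood tests | No |
| Kidney | BUN, creatinine, calculated GFR | No |
| Psychological state | Beck inventory at screening and visit 5 | No |

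An abnormal liver test or EKG is both a listed measure and an adverse event, so there is some overlap. Symptoms and allergic reactions fall outside it.

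**3. What the analysis set removes.** The protocol enrols 64 to obtain 50 completers, so it allows for 64 − 50 = 14 leavers, 14/64 = 21.9%. The permitted reasons for removal include allergic reaction, negative health effects and a severe adverse reaction. None of these subjects is in the SAP's analysis set.

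**4. Illustration with assumed counts.** The number dosed per arm is taken as 25 to 32 (25 completers per arm up to half of 64). Two-sided Fisher tests:

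- 6 against 0 with 32 per arm: p = 2 × C(32,6)/C(64,6) = 2 × 906,192/74,974,368 = 0.024.
- 8 against 1 with 32 per arm: p = 0.026.
- 6 against 0 with 25 per arm: p = 2 × C(25,6)/C(50,6) = 2 × 177,100/15,890,700 = 0.022.
- 9 against 2 with 25 per arm: p = 0.037.

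Take the first case and suppose that all six EMIQ subjects were withdrawn and everyone else finished. The completer set then holds 32 − 6 = 26 EMIQ and 32 placebo subjects, with 0 and 0 events. Even if someone tabulated adverse events in that set, the imbalance would be invisible.

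**5. Why a test alone would not be enough.** Power of Fisher's test at two-sided 0.05 to detect an excess on EMIQ, for assumed event rates:

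| Placebo vs EMIQ | 25 per arm | 32 per arm |
|---|---|---|
| 10% vs 30% | 31% | 41% |
| 20% vs 40% | 23% | 33% |
| 20% vs 50% | 51% | 64% |
| 10% vs 40% | 59% | 75% |

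A trebling from 10% to 30% would be missed more often than not, so a non-significant result could not stand as evidence of safety.

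**The case against.** A reader might infer that Hypothesis 2 is a closed list, that adverse events count for nothing, and that a clear excess on EMIQ would leave the safety hypothesis supported. The documents do not support that reading.

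- **The list is not declared exclusive.** Hypothesis 1 uses the same phrasing loosely: it includes physical activity and dietary intake, which do not measure fat, and does not name abdominal or visceral fat, which III.B says will be tested. The protocol also plans other safety tests, such as blood counts and electrolytes.
- **Adverse events do count for oversight.** They are reviewed weekly, summarised to the IRB and can contribute to stopping the study.
- **There is no decision rule.** Without a margin or criterion, no result formally supports or refutes Hypothesis 2.
- **The method exists.** The SAP's test for categorical variables could be applied to event counts.

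All four stand, and they limit the wording of the point. They do not close the gap. Wherever the supplied text says what answers Aim 2, adverse events are absent, and a generic test assigned to no safety variable, in completers, does not supply the comparison.

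Two further cautions stand. Enrolment is at visit 1 and capsules are first given out at visit 2, so 64 enrolled need not mean 64 dosed. The weekly log is described as a record that contact was made, so it may not be a ready adverse event dataset.

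**Conclusion.** The point holds in this form: the safety claim is general, the evidence named for it does not include adverse events, no by-arm comparison of them is specified, and the analysis set excludes subjects withdrawn for harm. An excess of symptoms, allergic reactions or event-related stops on EMIQ would not bear on Hypothesis 2 as written. Whether such an excess would leave the hypothesis supported cannot be said, because no criterion is set.

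The size cannot be derived from the documents. The event counts and rates above are illustrations only, and the 25 to 32 dosed per arm is an assumption. They show that at this sample size a visible imbalance is possible and that no named analysis would show it. One part of the SAP document was not available for review, so the conclusion is limited to the supplied text. The change should be made: the gap affects one of two specific aims, though not the efficacy analysis.

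**What to change.** Add to the evidence in Hypothesis 2, and to the SAP, the number and percentage of subjects in each arm with:

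- any adverse event;
- any serious adverse event;
- any adverse event leading to stopping the supplement.

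Count all randomised subjects who took at least one capsule, whether or not they completed. Report the between-arm risk difference with a 95% confidence interval for each row, and state that a non-significant difference is not proof of safety. Present the conclusion in section III.H only with this table beside it.

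If this is not done, limit the safety conclusion to the four named domains in completers.

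The cost is one clause, one SAP paragraph and one table. Weekly contact and event classification are already planned, but the team should confirm that events are recorded per subject in a form that can be tabulated. The downside is that the safety claim becomes harder to make. Withdrawal rules and clinical handling of events are not affected.
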